## **7.2. Illustration: pertussis dashboard**

Several sections below are taken directly from the POC1 protocol because POC1.2 will follow similar processes as POC1. To create a stand-alone document, but to avoid repetition for those familiar with POC1, we indicated the sections from POC1 with a \*. Readers familiar with POC1 might skip these sections.

### **7.2.1. Design**

This will be a dynamic cohort study. In a dynamic cohort subjects possibly enter or leave the cohort at any time during the study period.

### **7.2.2. Setting**

This POC 1.2 study will be conducted in six population-based healthcare databases from four European countries.

### **7.2.3. Databases/Data Sources**

The eligible data sources will be the eight European electronic health care databases from ADVANCE partners and associated partners that passed the POC1 feasibility assessment (see [Appendix 1](#)). In addition, these databases need to have the theoretical ability to generate periodic data. This information was collected through a face to face discussion and survey. This additional criterion reduced the number of databases that will participate to POC1.2 to six; ASLCR (Italy), ARS (Italy), PEDIANET (Italy), RCGP (UK), SIDIAP (Spain), SSI/AUH (Denmark). A description of the individual POC1.2 databases is given below.

#### ***Italy: ASL della provincia di Cremona (ASLCR)\****

ASLCR is a record linkage database. It contains all the mortality data (with cause of death), hospitalizations (with diagnosis), outpatient visits, drug prescriptions of the citizens. Moreover, it contains the registry of all the vaccinations administered by (or notified to) the Local Health Authority and the registry of infectious diseases to be notified by law.

---

The Local Health Authority (ASL) of Cremona is the institution in charge of the health of the citizens living in the province of Cremona. The ASL is responsible for the provision of all health-related services (prevention, treatment, residential care, etc.).

***Italy: Agenzia Regionale della Sanita Tuscany (ARS)\****

The ARS database contains health care data from the Tuscany region of Italy, including pharmacy, outpatient and hospital data along with linked data on death, and birth and malformation registries. Since 2017 the data is also linked to vaccination registries. The database is described in the ENCePP registry of datasources <http://www.encepp.eu/encepp/viewResource.htm?id=8133>

***United Kingdom RCGP\****

The RCGP's programme of influenza and respiratory disease surveillance has been supported by the Department of Health (DH) since 1967.

Between 1967 and 1993 the registered population within the RCGP RSC grew to 200,000 and it comprised 40 practices. By its 30th anniversary the population had risen to 570,000, with electronic links to general practices and laboratory data. The network exceeded 1million in 2015, and has now expanded to 237 general care practices and 2.4 million. From the start the network wanted clinicians to record a diagnosis in each consultation based on their clinical judgment; and only change that diagnosis if it adds to patient care. Diagnoses were originally recorded on paper written with "f", "n", or "o" written after- to designate first, new or an ongoing problem. This enabled incident and prevalent problems to be differentiated in routine data, vital for surveillance, but also for the Fourth National Morbidity Survey (MSGP4). High quality data recording was previously encouraged by visits to practices and quarterly feedback; now we apply principals of audit-based education to give practices personalized feedback on their data quality; we also provide use of on-line learning.

***Denmark: SSI/AUH\****

In Denmark national registry data are assembled and linked for specific studies according to the scientific question. Overall, the Danish Civil Registration System (CRS) database comprises individual level information on birth date, gender, vital status and sequential dates of migration of all residents in Denmark, i.e. approx. 5.6 mill. persons in a year, and an accumulated number of approx. 7.5 mill. persons over the period 1996-2014. Hence, using a unique personal identifier assigned to all Danish residents upon birth or immigration makes it possible to link the CRS with health care databases such as the Danish Vaccination Registry (DVR) and the Danish National Patient Registry (DNPR).

The national childhood vaccination database was established in 2000. This comprises information on all vaccinations administered to children below the age of 18 years, including vaccinations recommended by the Danish childhood vaccination programme, such as HPV, influenza etc. From November 2015, GPs and

---

others authorized to vaccinate have an obligation to record all vaccinations, and this information is now merged with data that were compiled before 2015 into the Danish Vaccination Registry.

The Danish National Patient Registry has recorded every inpatient hospitalization since 1977, and every outpatient and emergency room visit since 1995. For each admission, one primary and potentially several secondary diagnoses are registered, classified according to the *International Classification of Diseases, Eighth Revision* (ICD-8) until the end of 1993, and *Tenth Revision* (ICD-10) thereafter. In Advance this database is used to identify events.

While CRS and DVR are updated on a daily basis, DNPR have a delay of up to 3 months. The data are kept at the Research Services at the SSI from where access can be granted provided that the analysis has been reported and approved by the Danish Data Protection Agency. There is a long tradition of epidemiological studies in Denmark based on the health care databases that were proven valid for research.

### **Spain: SIDIAP\***

The Information System for Research in Primary Care (SIDIAP; [www.sidiap.org](http://www.sidiap.org)) contains information recorded in anonymized patients' electronic health records for nearly six million people (approximately 75% of the Catalan population) since 2005 by 286 primary care practices of the Catalan Health Institute throughout Catalonia. It was designed to provide a valid and reliable database of selected information from clinical records of patients registered in primary care centres for use in biomedical research. SIDIAP population is highly representative of the entire Catalan region in terms of geographic, age, and sex distributions. It includes data collected by health professionals in Catalonia during routine visits in primary care, including clinical diagnoses (International Classification of Diseases 10th revision [ICD-10]), laboratory test results, prescribed and dispensed drugs, vaccination, hospital referrals, anthropometric and other measurements performed during routine visits, demographic and lifestyle information. Quality checks to identify duplicate patient IDs are performed centrally at each SIDIAP data base update, which is done annually. Checks for logical values and data harmonisation are performed. For biochemistry data, consistency for measurements taken in different laboratories is assessed, and unit conversion is undertaken when needed. The high quality of these data has been previously documented, and SIDIAP has been successfully applied to epidemiological studies of key exposures and outcomes. SIDIAP is listed in the ENCePP registry of datasources: <http://www.encepp.eu/encepp/viewResource.htm?id=4646>

---

 Bolívar, B. et al. [SIDIAP database: electronic clinical records in primary care as a source of information for epidemiologic research]. *Med. Clínica* 138, 617–621 (2012).

García-Gil, M. D. M. et al. Construction and validation of a scoring system for the selection of high-quality data in a Spanish population primary care database (SIDIAP). *Inform. Prim. Care* 19, 135–145 (2011).

Ramos, R. et al. Validity for use in research on vascular diseases of the SIDIAP (Information System for the Development of Research in Primary Care): the EMMA study. *Rev. Esp. Cardiol. Engl. Ed* 65, 29–37 (2012).

**Italy: Pedianet\***

Pedianet ([www.pedianet.it](http://www.pedianet.it)) is a longitudinal observational DB that collects epidemiological clinical data for clinical research from family paediatricians involved in the Pedianet network in Italy. This system is based on the transmission of specific data from computerised clinical files, which the paediatricians in the network fill out during their daily professional activities. Informed consent is required from the parents. Such data is collected anonymously by a central server in Padua, where it is validated and elaborated.

Pedianet is an independent network. The coordination of the projects and data analysis is carried out by a scientific committee that include internationally renowned paediatricians, epidemiologists and researchers. Approximately 400 paediatricians throughout the country have taken part in Pedianet projects.

The paediatric population involves infants, toddlers, children and adolescents up to 14 years. The DB contains information on about 400 000 patients. This is the cumulative amount of patients who have ever been part of the dynamic cohort of patients who have been registered.

Pedianet includes primary care diagnoses, outpatient specialist diagnoses, hospital discharge diagnoses, prescribed drugs, vaccinations and laboratory test results.

In order to provide more comprehensive and validated data, linkage with external Regional databases, including hospitalizations, vaccinations and specialist visits/exams, is ongoing. PEDIANET is involved in several EU funded projects including TEDDY, GRIP, EU-ADR, EMIF and SOS. For the ADVANCE project, PEDIANET has linked the birth cohorts of 2006 and 2007 to the Regional Vaccination Register of Veneto on 9000 children. Linkage of subsequent birth cohorts is ongoing once consent is obtained from the subjects. Pedianet is listed in the ENCePP registry of datasources (<http://www.encepp.eu/encepp/viewResource.htm?id=20131>)

#### **7.2.4. Study Population**

All children from start of follow-up in their database until end of follow-up within the eligible ADVANCE databases. Start of follow-up will be the latest of: start of the study (i.e. 01 January 2014), first date of registration in the database, date of birth. End of follow-up will be the earliest of: death, end of registration in the database or moving out, receipt of pertussis booster dose, reaching 6 years of age, or data lock point.

---

Prieto-Alhambra, D. et al. Relationship between mortality and BMI after fracture: a population-based study of men and women aged  $\geq 40$  years. *J. Bone Miner. Res. Off. J. Am. Soc. Bone Miner. Res.* 29, 1737–1744 (2014).  
Garcia-Gil, M. et al. Linking of primary care records to census data to study the association between socioeconomic status and cancer incidence in Southern Europe: a nation-wide ecological study. *PLoS One* 9, e109706 (2014).  
Incidence and risk factors for clinically diagnosed knee, hip and hand osteoarthritis: influences of age, gender and osteoarthritis affecting other joints. *Ann. Rheum. Dis.* 73, 1659–1664 (2014).

---

Children will be excluded if at least one of the following variables is missing: date of birth, date of start of follow-up (date the patient is entered into the registration system) and date of end of follow-up (e.g. end of registration, moving out, death, last data draw down - whichever is earliest).

### **7.2.5. Study Period**

The study period will consist of two distinct periods. The first period will start from 01 January 2014 until the start of the near real-time monitoring and has as objective to establish a baseline. The second period is the actual near real-time monitoring which will start upon approval of the protocol by the institutional review board/independent ethics committee/research ethics board (IRB/IEC/REB). The period of near real-time monitoring will cover a minimum of 3 data loads and be maximum 3 months long.

It should be noted that the start of follow-up for the POC1.2 study period is arbitrary and was selected to ensure an observation period long enough to obtain stable rates while also minimizing the computational burden. This arbitrary date does not correspond in any way to a date where there would be a need or a trigger to start monitoring (as in normal use of a monitoring system). The same principles apply to the date that will be used for the start of the short period of near real time monitoring.

### **7.2.6. Variables**

#### **7.2.6.1. Common Data Model (CDM)\***

Each study database will create three input files in the pre-defined study-specific ADVANCE common data model (CDM): a population, event and vaccination input file (see [Appendix 2](#)). All three data files will use the same unique, encrypted person identifier to allow linkage across the database-specific CDM input files.

#### **7.2.6.2. Exposure of Interest, Operationalization and Validation**

##### **EXPOSURE OF INTEREST**

The exposure of interest is any acellular pertussis-containing (aP) vaccine used by the study population covered by the ADVANCE databases participating in POC1.2.

##### **OPERATIONALIZATION**

---

Vaccinations will be obtained from the databases using vaccine names and database specific codes (Appendix 3). Only data on aP vaccines will be retrieved, and there will be no stratification by vaccine brand or product name.

#### **VALIDATION**

Validation will be done according to fingerprinting methodology developed in ADVANCE (ADVANCE sharepoint: WP5 deliverables D5.2) The vaccine fingerprinting process (characterizing the data in a systematic manner) comprises the following components: 1) assessment of rounding of birth dates, 2) assessment of the concordance between doses and recommended country specific schedules; 3) Assessment of coverage against country specific benchmarks (WHO or national data).

### **7.2.6.3. Outcomes, Operationalization and Validation**

#### **OUTCOMES**

The risk outcomes of interest will be the same as in POC 1. However, injection site reactions and generalized convulsions were excluded. The exclusion of injection site reactions is based on the experience of POC 1, which demonstrated that many participating databases were able to extract general skin and muscle related events, signs and symptoms that potentially were not occurring at an injection site. The absence of "injection site" related information in some databases resulted therefore in a broad spectrum of extracted skin and muscle events, signs and symptoms that have been considered to be too sensitive and not specific enough to be further included as potential adverse events of interest in the POC 1.2. Generalized convulsions have been excluded because the experience from POC 1 showed that febrile convulsions/seizures dominated the entity of the convulsions/seizures. As most of the databases provided highly specific codes for the identification of febrile convulsions/seizures, we decided to continue with febrile convulsions/seizures only. The outcomes of interest (and associated risk windows) are listed in the Table 1. The benefit outcome is confirmed or probable pertussis.

---

**Table 3: Outcomes of interest and risk windows**

Outcome	Risk Window After Vaccination/*start of protection
Risks	
Fever	0-72 hours
Somnolence	0-48 hours
Persistent crying, irritability	0-24 hours
Febrile convulsions/seizures	0-72 hours
HHE	0-48 hours
Benefits	
Pertussis	*2 wks after vaccination

#### **OPERATIONALIZATION\***

Outcome events will be obtained from the databases using diagnosis codes or free-text proxies (code lists as in POC1 listed in [Appendix 4](#)).

#### **VALIDATION**

Semantic harmonization of events into different coding dictionaries was conducted using the ADVANCE Codemapper [3]. All events are benchmarked by assessing age-specific incidence rates and comparison of these rates between the databases in the consortium, as well as against published data. For the POC1.2 eligible databases, this process was conducted successfully as part of their quality assessment.

#### **7.2.6.4. Other Variables and Operationalizations**

The incidence rates of the benefit and risk outcomes will be stratified by calendar time and country. The unit of stratification by calendar time will be weeks to allow for timely monitoring.

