#### **Data analyses**

The test case is near real-time (weekly or bi-weekly/monthly, depending on the database) visual monitoring of vaccination coverage, benefits and risks of pertussis vaccination. The monitoring will be facilitated through the use of an interactive dashboard developed based on the POC1 data. The dashboard contains three monitoring tabs with visualizations:

- Coverage: number of administered doses per week over calendar time (extrapolated to the population of interest) and vaccination coverage (%) within specific age groups by calendar time
- Benefits: observed pertussis incidence in the total population by calendar time
- Risks: incidence rates in event specific risk windows and in control periods (out of risk windows) at vaccination eligible ages, separately for each risk outcome by dose, estimated cumulatively over calendar time.

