### 7.2.7.5. Statistical Methods

In POC1.2, the objective is near real-time visual monitoring of vaccination coverage, benefits and risks using aP vaccination as the test case. As such, we will monitor epidemiological measures including, vaccination coverage and incidence rates as they evolve over time. The monitoring will be facilitated through the use of a “Shiny” web-application [4] with a user-friendly interactive dashboard containing three monitoring tabs for visualization of coverage, benefits and risks. This dashboard will be interactive and allow for inter-country comparisons.

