**Benefits: line plots with pertussis incidence and 95% confidence intervals over time**

The pertussis incidence (/100.000 person-years) will be calculated as the number of pertussis events divided by the total person-time at risk for week  $i$  multiplied with 100.000. Exact Poisson 95% confidence intervals will be calculated.

**Risks: line plots with incidence of risk outcomes inside and outside the risk window and 95% confidence intervals over time using accrued data**

The incidence rate (per unit person- years) for the risk outcomes within the pre-defined, outcome-specific risk windows will be estimated by week. In addition, the incidence rates will be estimated cumulatively over time, using all data accrued from the start of the study period until week  $i$  or

$$inc_i = \left( \frac{\sum_{i=1}^i n_i}{\sum_{i=1}^i py_i} \right) \times \text{unit person years}$$

where  $n_i$  is the number risk events of interest that happened during week  $i$  and where  $py_i$  is the amount of person-time (in years) within that week. Incidence rates outside the risk windows in vaccination comparable age groups will be calculated as well. Each time, exact Poisson 95% confidence intervals will be calculated.

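### The benefit tab plots one crude pertussis rate per week and country, although follow-up ends at the booster, so inter-country differences may partly reflect the age mix of the person-time

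*Protocol*

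**What the plan says.** - **Strata.** Protocol 7.2.6.4: "The incidence rates of the benefit and risk outcomes will be stratified by calendar time and country". The calendar unit is the week. Age is not named.
- **Rate.** Protocol 7.2.7.5, Benefits paragraph: the pertussis incidence "will be calculated as the number of pertussis events divided by the total person-time at risk for week" *i*, scaled to 100,000 person-years, with an exact Poisson interval. The Abstract describes the same tab as "Benefits: observed pertussis incidence in the total population by calendar time".
- **Who contributes person-time.** Under 7.2.4, follow-up starts at the latest of "start of the study (i.e. 01 January 2014), first date of registration in the database, date of birth". Apart from death or leaving the database, it ends at the earliest of "receipt of pertussis booster dose, reaching 6 years of age, or data lock point".
- **Schedules.** The vaccine validation step in 7.2.6.2 includes "assessment of the concordance between doses and recommended country specific schedules".
- **Purpose of the display.** Protocol 7.2.7.5: "This dashboard will be interactive and allow for inter-country comparisons".

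Age is taken into account elsewhere. Coverage is computed by age group and by birth-month cohort (7.2.7.5). Risk-outcome rates outside the windows are restricted to comparable ages (7.2.7.5). Event benchmarking between databases uses age-specific rates (7.2.6.3). Section 7.2.7.1 describes each database population by age group, but no plotted rate is adjusted with that table.

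**The concern.** A crude rate is an average of age-specific rates weighted by person-time at each age. Here the weights depend on when, and how completely, children receive the booster that ends their follow-up. If one country boosts earlier or with higher uptake, its older children leave the denominator sooner and its person-time is younger. If pertussis incidence varies with age over 0 to under 6 years, two countries with the same disease at every age then show different curves on the benefit tab.

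At stake is the comparison for which the tab is offered. Chance error shrinks as weeks accumulate, but a difference caused by age mix does not. It also cannot be undone on the dashboard. Under 7.2.9.2 and 7.2.9.3 the data are aggregated locally and only summary tables are transferred, so an age dimension left out of those tables cannot be recovered there.

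**Working it through.** The protocol states no figure for this effect, so there is nothing to reproduce. The check asks how far the planned crude rate can differ between two countries whose age-specific rates are identical.

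**Inputs from the protocol.** Crude rate by week and country (7.2.6.4, 7.2.7.5); exit at booster or age 6 (7.2.4); reference person-years of about 37,000 a year for RCGP and 220,000 for SSI, and a lowest planning incidence of 2 per 10,000 person-years (7.2.7.4).

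**Assumed inputs, because the protocol gives none.** Exit age *A*; booster uptake *u*; ratio *r* of the pertussis rate under 1 year to the rate from 1 year on; equal person-time per year of age.

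**Step 1: complete uptake.** Relative to the older-age rate, the crude rate for exit at age *A* is f(A) = (r + A − 1)/A.

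| r | f(4) | f(6) | f(4)/f(6) | f(5)/f(6) |
|---|---|---|---|---|
| 1 | 1.000 | 1.000 | 1.00 | 1.00 |
| 2 | 5/4 = 1.250 | 7/6 = 1.167 | 1.07 | 1.03 |
| 3 | 6/4 = 1.500 | 8/6 = 1.333 | 1.125 | 1.05 |
| 5 | 8/4 = 2.000 | 10/6 = 1.667 | 1.20 | 1.08 |
| 10 | 13/4 = 3.250 | 15/6 = 2.500 | 1.30 | 1.12 |

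**Step 2: incomplete uptake.** Children without a booster stay until age 6. Older person-time becomes p = (A − 1) + (1 − u)(6 − A), and the relative crude rate is (r + p)/(1 + p). With u = 0.9 and A = 4, p = 3 + 0.1 × 2 = 3.2. For r = 5 this gives 8.2/4.2 = 1.952, and 1.952/1.667 = 1.17 instead of 1.20. For r = 10 it gives 13.2/4.2 = 3.143, and 3.143/2.5 = 1.26 instead of 1.30.

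**Step 3: which booster ends follow-up.** The target population in the Abstract refers to the booster at school entry, whereas 7.2.4 refers to a pertussis booster without that qualifier. The vaccination file in Appendix 2 allows more than one booster number. Suppose any booster ended follow-up in one country (assumed age 1.25) and a later one did in another (assumed age 5), with u = 0.9. The ratio would then be 1.32 for r = 2, 1.86 for r = 5 and 2.25 for r = 10. The two descriptions therefore imply very different age spans.

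**Step 4: the same scenarios after standardisation.** With fixed weights of 1/6 (under 1 year) and 5/6 (older), the rate is (r + 5)/6 in both countries whatever the exit age or uptake. The ratio is 1.00 for every r.

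**Step 5: chance error for comparison.** If pertussis lies at 2 per 10,000 person-years (an assumption), RCGP expects 37,000 × 2/10,000 = 7.4 events a year, or 7.4/52 = 0.14 a week. SSI expects 44 a year, or 44/52 = 0.85 a week. The 95% limits of the SSI-to-RCGP rate ratio extend by a factor of exp(1.96 × √(1/7.4 + 1/44)) = 2.18 after one year. After 4.25 years (January 2014 to March 2018) the factor is 1.46. Single weeks are dominated by noise. The age effect would matter, if at all, over long accrual or at higher rates.

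**The case against.** The strongest reply is that the premise is only half documented. The protocol says that schedules are country specific, but gives no booster ages and does not say that those ages differ. A reader might infer that the age span differs by construction. The text supports only that it may differ. If the exit is the school-entry booster, the spread may be small. If incidence does not vary with age, the effect is nil. This part of the reply stands.

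It also stands that the study is a system test. Section 7.2.7.3 rules out formal testing, the disclaimer excludes regulatory and clinical use, and none of the four measures of success in 7.1 depends on the level of the pertussis rate. A reader might infer that a distorted curve would be taken as a difference in vaccine benefit. The documents do not establish that. Section 7.2.8 already warns that data provenance can make databases differ, and age adjustment would not remove that.

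Two further replies stand only in part. The age table in 7.2.7.1 helps a reader understand differences between databases, but corrects no plotted rate. A statistical analysis plan could add age strata, and 7.2.6.4 does not forbid them. The protocol nevertheless names the strata and the calculation, and those as written give a crude rate.

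The objection to weekly standardisation over single years of age is right: with 0.14 to 0.85 expected events a week, most cells would be empty.

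**Conclusion.** The point holds in a limited form. As specified, the benefit tab compares countries on a crude rate whose age composition depends on booster timing and uptake, so curves can differ although age-specific rates are identical.

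Under complete uptake and equal person-time per year of age, exit at 4 instead of 6 gives a spurious excess of 0%, 7%, 12.5%, 20% or 30% for a rate ratio of 1, 2, 3, 5 or 10. Exit at 5 instead of 6 gives 0% to 12%. Incomplete uptake reduces these figures. All of them rest on assumed exit ages and rate ratios. The direction in practice is unknown, because the protocol shows neither which country has the younger person-time nor how incidence changes with age.

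The effect is confined to a descriptive comparison. Trends within a country are less affected as long as its booster timing and uptake are stable. The change is still worth making before the local programs are fixed, because age cannot be added once only summary tables have been transferred.

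**What to change.** 1. Amend 7.2.6.4 and the Benefits paragraph of 7.2.7.5 so that pertussis events and person-time are aggregated locally by week, country and a coarse age band, for example under 1 year and from 1 year to the youngest exit age common to all countries.
2. Keep the weekly crude rate with its exact Poisson interval for monitoring within a country.
3. For comparisons between countries, show age-band rates, or a rate standardised to one fixed set of age weights, over pooled or cumulative periods rather than single weeks. State the interval method for the weighted rate, since the simple exact Poisson interval no longer applies to it.
4. Label the crude curves as not age-comparable between countries.
5. Reconcile the Abstract and 7.2.4 on which booster ends follow-up, since the reading determines the age span.

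The cost is a change of wording and one more stratum in the local tables; date of birth is already in Patients.txt (Appendix 2). Cells become sparser, and intervals for the age-band or standardised rates become wider. A coarse band removes the age effect fully only if incidence is roughly constant within each band. It does not address differences in data provenance.
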